Although the ultimate goal of using WATs should be increased MVPA, such data was not reported in previous studies on older people. Moreover, the suggested additional measures for facilitating the adoption of WATs by older people have not previously been tested. It is worth testing the efficacy of a combined intervention of exercise training plus WAT intervention in which BCTs have been incorporated. Little is presently known about the efficacy of using a WAT intervention among older people with frailty. The main hypothesis is that the WAT intervention plus exercise training programme will increase physical activity levels compared to an exercise programme alone. If we are successful in proving the hypothesis, we will propose studying the long-term effects (i.e., increased daily MVPA and the adoption of a physically active lifestyle) of this intervention in the main study with a larger sample size with a longer follow-up period.

B. Research plan and methodology (Appendix 1: Consort Research Flowchart)

Aim: A single-blinded, repeated-measures, two-arm pilot cluster RCT is proposed to examine the feasibility and preliminary effects of an exercise programme with or without a WAT intervention for promoting physical activity levels among community-dwelling older people with frailty. To explore the acceptability of the WAT intervention, a focus group with all participants in the experimental group (4-6 people per group) will be interviewed by JS (the Co-I).

Subjects and Settings: A district community health centre will be viewed as one unit/cluster. Eligibility criteria for district community health centres are those that are funded by the Hong Kong (HK) government and under the supervision of the Social and Welfare Department of HK, and thus that meet a specific set of standard regulations and criteria on environment and practices. Six community centres, which provide similar types of community care and social support services for community-dwelling older people, will be invited by a convenience method to work as collaborators in this study. The target population of this study are community-dwelling older people with frailty who will be recruited through the community centres.

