Sample size: Teare et al., 2014 recommended that a pilot study is required a total number of participants between 60 and 100 when estimating the effect size for a continuous outcome. Thus, sixty participants will be recruited from six community centres. We estimate that about 25-50% of the members of these centres will be eligible to participate (Schultz-Larsen et al., 2007; Liu, 2017). We will target moderate to large centres with the total number of centre members around 800. Given that we can screen 200 older people (50 in each centre) per 4 to 6 weeks, and based on our previous study in similar centres (Liu et al., 2017), we believe that we will need about 3 to 4 months to recruit 60 participants (with 30 subjects recruited per 4 to 6 weeks in two-three centres) for this study. Given the difficulty of obtaining details of the backgrounds of all potential participants in these community settings, a properly random sample cannot be implemented. Thus, convenience sampling will be used to recruit participants among the collaborative community centres. Using computer-generated random numbers, a biostatistician not affiliated with this study will randomize the centres in a 1:1 ratio into either: the control or the experimental groups. Participants from each centre will be placed in their centre's corresponding group to avoid 'contamination' effects across participants. To avoid selection biases, the allocation to the study groups will be concealed from the researchers until sample recruitment and baseline measurements have been completed. Appendices 1 and 2 show the CONSORT research flow chart and the timeline of this study.

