The Control Condition: The same physical training and BCTs support will be arranged for the control group.

Instruments and Measures:

Participants will be assessed on a variety of outcomes (described below) at 1 week and at 1 and 3 months (T1 – T3) after the programme, which will be compared with the baseline assessment (T0). The participants will be asked to wear an ActiGraph Wgt3x accelerometer on their non-dominant wrist for 7 days before the commencement of any intervention, as well as during each outcome assessment time point.

Socio-demographic data: The following data will be collected: 1) data on age, gender, marital status, exercise habits, living conditions, and level of education, 2) the participants' health-related information, including their morbidities, cognitive status, medications, and number of hospital and out-patient clinic visits in the past 12 months.

Feasibility:

To understand the feasibility of this intervention, the frequency with which the participants in the experimental group use the tracker over the time of the study (i.e., 112 days), the recruitment rate, the attrition rate, the participants' adherence to the exercise regimen, and reports of adverse effects will be monitored.

Primary outcome measurement: Activity levels

The participants' physical activities and sedentary time will be objectively measured using a ActiGraph wGT3X accelerometer.

Secondary outcome measurements

Fitbit Data (only participants in the experimental group): The total steps per week, total walking distance per week, and time spent in different heart rate zones (50-69%, 70-84%, and >85% of the maximum heart rate) of an individual will be collected.

Physical Endurance: This will be evaluated using different physical tests:

1. The participants' lower-limb muscle and upper-limb strength will be assessed using a 30-second chair stand test and a handheld Jamar Hydraulic Hand Dynamometer, respectively.
2. Mobility will be assessed through the Timed-up-and-Go (TUG) test and by their gait speed (2-m walk). These two tests assess the overall performance of the lower limbs and walking speed, which can reflect the effect of exercise in enhancing the participants' overall physical endurance.

Exercise Self-efficacy: The participants' self-confidence in their ability to exercise in a variety of circumstances (e.g., even when they were feeling tired) will be assessed using the Chinese Self-Efficacy for Exercise scale (CSEE).

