Official Title: Enhancing physical activity levels of community-dwelling older people with frailty through an exercise intervention with or without a wearable activity tracker (WAT)-based intervention: a feasibility and pilot study

Date of the document: 22/03/2018

Approved by the Human Subjects Ethics Sub-committee of The Hong Kong Polytechnic University on 13/04/2018

Statistical Analysis:

SPSS version 23.0 will be used to analyse the data. Descriptive statistics will be generated for the demographic data and feasibility tests. The baseline characteristics of the participants in the two groups from the six community centres will be compared using unpaired t test for the continuous variables, a chi-square test for the categorical variables, and the Mann-Whitney U test for the ordinal variables. Normality assumptions for the variables will be examined by a K-S test. The group attendance and drop-out rate of the participants in the study groups will be reported. An intention-to-treat analysis will be adopted. An independent sample Student's t-test or Mann-Whitney U test will be used to examine differences between the control and experimental groups in the outcome variables. For categorical and dichotomous outcome variables, an χ^2 test will be used to test differences between the groups. If significant differences between the groups at baseline have been identified, these data will be treated as covariates and adjusted for as needed. A p-value of < 0.05 will be considered statistically significant. ANOVA will be used to measure the effectiveness of the intervention. If the data were non-normal, Friedman's test will be used instead. Post-hoc within-group comparisons will be done using paired t-tests or Wilcoxon's signed rank test, and Bonferroni adjustments will be made.

Content analysis will be used to analyse the interview data. All audio-taped interviews will be transcribed into Cantonese by the RA and the transcriptions will be checked for accuracy by two members of the research team before the analysis.

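### The only stated route to the main study is proof of superiority, which a 60-person, six-centre pilot chosen to estimate an effect cannot settle reliably in either direction

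*Protocol*

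**What the plan says.** The last paragraph of the Protocol's Background states: "The main hypothesis is that the WAT intervention plus exercise training programme will increase physical activity levels compared to an exercise programme alone". The next sentence makes further work follow from that result: "If we are successful in proving the hypothesis, we will propose studying the long-term effects". Neither document contains any other statement about moving to a main study.

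The rest of the plan describes a different purpose. Under Aim, a "two-arm pilot cluster RCT is proposed to examine the feasibility and preliminary effects" of the programme. Under Sample size, the Protocol cites a simulation study which "recommended that a pilot study is required a total number of participants between 60 and 100 when estimating the effect size for a continuous outcome", and from this concludes that "sixty participants will be recruited from six community centres". A biostatistician "will randomize the centres in a 1:1 ratio into either: the control or the experimental groups".

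The Feasibility section lists tracker use in the experimental group, "the recruitment rate, the attrition rate", adherence to the exercise regimen and adverse effects. It gives no thresholds and no link to progression. The SAP treats the feasibility data descriptively. It compares groups with an individual-level t-test or Mann-Whitney test and adds: "A p-value of < 0.05 will be considered statistically significant".

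**The concern.** The aim and the sample size belong to a pilot that estimates; the progression sentence belongs to a trial that tests. A team following that sentence would decide on the main study from an efficacy result that the pilot was not sized to deliver. The measures that a pilot of this size can inform directly (recruitment, retention, adherence, tracker use) would have no stated part in the decision.

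Two wrong decisions are possible. A useful intervention may fail to reach significance and be dropped. An ineffective one may reach significance because the planned test ignores the centres that were randomised. In addition, if the effect estimate is carried forward only when significant, it is too large on average, and a main trial sized on it would be too small.

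**Working it through.** **Inputs from the documents.** 60 participants and six centres randomised 1:1 (Protocol, Sample size), so 30 per arm and 10 per centre if equal; significance at p < 0.05 and an individual-level t-test with no centre term (SAP).

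**Assumed, because the documents do not say.** Proof means p < 0.05; two-sided; true effect d = 0.3 to 0.8 SD; ICC 0 to 0.10; no attrition and no baseline adjustment unless noted.

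**1. The plan's own figure.** 60 lies at the lower end of the cited range of 60 to 100. No effect size, SD, power or ICC is given, so no power formula can reproduce it.

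**2. The SAP's t-test, centres ignored, ICC 0.** Standard error in SD units = √(2/30) = 0.258; 58 df; critical t = 2.002; noncentrality = d/0.258. For d = 0.5 this is 1.936, and power from the noncentral t is 0.478.

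| True d | Chance of p < 0.05 |
|---|---|
| 0.3 | 21% |
| 0.4 | 33% |
| 0.5 | 48% |
| 0.6 | 63% |
| 0.8 | 86% |

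The earlier pilot described in the Background lost 7.1%. The same loss here leaves 30 × 0.929 ≈ 28 per arm, and the chance becomes 45% at d = 0.5 and 84% at d = 0.8.

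**3. If baseline were adjusted for.** The standard error is multiplied by √(1 − r²), with 57 df. At d = 0.5:
- r = 0.5: standard error 0.224, noncentrality 2.236, power 59%.
- r = 0.7: standard error 0.184, noncentrality 2.712, power 76%.

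Both correlations are assumed.

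**4. A test that respects the centres (not planned in the SAP).** Variance of the difference in mean centre values = (ICC + (1 − ICC)/10) × 2/3; 4 df; critical t = 2.776.

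| ICC | Standard error | d = 0.3 | d = 0.5 | d = 0.8 |
|---|---|---|---|---|
| 0 | 0.258 | 15% | 32% | 65% |
| 0.05 | 0.311 | 11% | 24% | 50% |
| 0.10 | 0.356 | 10% | 19% | 40% |

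**5. No true effect, SAP's t-test with centres ignored** (simulation, 200,000 trials per ICC). It is significant in about 6%, 10% and 16% of trials at ICC 0.01, 0.05 and 0.10. These rates count both directions. About half (3%, 5% and 8%) favour the tracker and would be a false go, against a nominal 2.5%. This is for one variable at one time point. The Protocol plans activity and sedentary time at three post-programme visits, without naming a primary one.

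**6. Inflation when only significant estimates are used** (SAP's t-test, ICC 0). The smallest significant effect is 2.002 × 0.258 = 0.517 SD. With a true d of 0.5, the cut-off lies (0.517 − 0.5)/0.258 = 0.065 standard errors above the truth. The mean of the significant estimates is 0.5 + 0.258 × φ(0.065)/(1 − Φ(0.065)) = 0.5 + 0.258 × 0.840 = 0.72 SD (0.71 by simulation). A trial sized on 0.72 would have (0.5/0.72)² ≈ 0.48 of the participants needed. At a true 0.8 SD the simulated mean is 0.87, only 1.08 times the truth. With baseline adjustment at r = 0.5 or 0.7, the mean for a true 0.5 SD falls to 0.65 or 0.58.

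**The case against.** The strongest reply is that the plan contains no go/no-go rule. The sentence stands in the Background, says if and not only if, does not say what follows a null result, and is not repeated in the research plan or the SAP. No variable, visit or test is named for the proof, and the 0.05 level in the SAP is a general convention that is not tied to progression. The Background also reports an earlier 85-person pilot in which the authors put non-significant outcomes down to small numbers, stressed feasibility and went on to propose further work. That was a different intervention, and its attendance and compliance results were significant, but it suggests that the authors would not treat an underpowered null as a rejection.

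Most of this stands, and it limits the claim. A reader might infer that the pilot is bound to reject most worthwhile interventions. The documents do not support that: they give no effect size, SD or ICC. Under the SAP's own t-test a true 0.5 SD is close to a coin toss, 0.6 SD passes 63% of the time and 0.8 SD passes 86%. The design has a baseline accelerometer week, and if the analysis used it the chance at 0.5 SD would exceed one half; the SAP does not spell this out. The lower centre-level figures belong to a test that is not planned. A reader might also infer that the main trial will be undersized, but neither document says how it would be sized.

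The objection does not remove the conflict of purpose. The only condition written down is efficacy, and the feasibility measures carry no stated weight.

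**Conclusion.** The point holds in a limited form. The single progression statement rests on proving superiority, which does not match an aim of feasibility and preliminary effects or a sample chosen for estimation. If proof means p < 0.05, the result is an unreliable guide in both directions. Real effects of 0.3 to 0.5 SD are missed in about half to four-fifths of trials under the SAP's t-test at ICC 0 without baseline adjustment, and false positives exceed the nominal rate once centres differ. Inflation of a significant estimate is material for moderate effects and small for large ones.

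These sizes depend on the assumed effects, ICCs and reading of proof. The mismatch between the sentence and the stated purpose does not. It does not affect how participants are treated or what data are collected, so it ranks as a cheap improvement.

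**What to change.** Replace the closing sentence of the Background so that progression rests on the measures already listed under Feasibility: recruitment, attrition, adherence and tracker use. The team should set numeric thresholds before allocation is revealed. The recruitment threshold is best set before recruitment starts, because allocation stays concealed until recruitment and baseline measurement are complete.

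In the SAP, report the activity difference with a 95% confidence interval that respects the centres, together with the between-centre variance. With six centres both will be imprecise, and the report should say so. State that statistical significance is not a condition for proposing the main study.

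The cost is wording in the two documents and one added analysis; no further participants or data are needed. The downside is that the team gives up the claim that this pilot can prove efficacy.

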Wearable fitness trackers (WAT) are activity monitors that track daily activity levels and synchronize the data (such as step counts, time spent on MVPA, heart rate, calories burned) to smartphone applications. WAT technologies are increasingly accessible and offer the potential to support lifestyle interventions targeted at enhancing physical activity. It is believed that the mechanism that makes WATs effective at increasing the physical activity of older people relates to increasing their self-efficacy. Previous systematic reviews have identified a significant correlation between physical activity self-efficacy and different BCTs (French et al., 2014). Some of these effective BCTs have already been incorporated into the design of the WATs, such as “prompting a review of behavioural goals”, “providing rewards contingent upon successful behaviour”, “alerting self-monitoring of behaviour”, “encouraging a focus on past successes”, and “giving cues to action” (Mercer et al., 2016). For instance, “cues to action” are important if sedentary behaviour is to be replaced with physical activity, as they provide real-time prompts to alert the participants of the need to avoid sedentary behaviour. In addition, the capacity for the user’s behaviour to be shared via the connectivity capabilities of smartphone applications can promote social support, feedback, and competition via social networking platforms (Nakhisi, 2014). Another systematic review has shown that activity monitors can positively influence multiple health behaviours, including physical activity (Fanning, 2012). These are important elements in changing and maintaining the change in behaviour (French et al., 2014).

Before the availability of this technology, to implement these BCTs required well-trained instructors to continually conduct face-to-face or telephone sessions with the participants. It was highly likely that these elements would gradually fade out after the completion of the face-to-face or telephone programme. With advancements in technology, these important BCT elements are already embedded in the WATs. It is believed that even after the completion of the programme, users of WATs have a greater chance of adopting the BCTs and of maintaining a physically active lifestyle over the long term.

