The Inclusion Criteria are: 1) community-dwelling older people aged ≥ 65 years; 2) able to communicate in Cantonese to ensure that they understand our instructions; 3) able to walk with or without an assistive device and able to complete the Time Up and Go (TUG) test with no specific cutoff point to ensure that their mobility and balance is good enough to join the exercise training; 4) able to use a smartphone; and 5) in a pre-frail or frail state as determined using the Fried Frailty Index^[1]; including: i) having experienced an unintentional loss of 10% of body weight in the past year; ii) exhaustion: by answering 'Yes' to either 'I felt that everything I did was an effort', or 'I could not get going in the last week'; iii) a slow walk time: with an average walking speed in the lowest quintile stratified by median body height; iv) reduced grip strength: with maximal grip strength in the lowest quintile stratified by the body mass index quartile; and v) a Physical Activity Scale for Elderly-Chinese (PASE-C) score in the lowest quartile (i.e., < 30 for men and < 27.7 for women). The presence of 1-2 indicates pre-frailty, ≥ 3 items indicates frailty.

The Exclusion Criteria are older people who: 1) have any physical conditions that hamper their performance of the exercise programme or use of the WAT, such as visual or hearing problems. 2) regularly engage in moderately intense exercise (such as hiking, Tai Chi) for ≥ 3 hours per week.

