Interventions: A 3-month exercise programme plus WAT intervention will be arranged for the participants in the experimental group. They will receive a weekly centre-based exercise programme for 3 months. Meanwhile, two face-to-face sessions followed by weekly to monthly telephone sessions offering support on dealing with technical issues and BCTs will be arranged for the experimental group (see Figure 1: Intervention components for the experimental group). The additional technical support given alongside the WAT intervention will be gradually withdrawn from the participants. Eventually, all additional measures to support the use of WATs among participants will be stopped. Participants will be left to use the WAT on their own for 3 months during the follow-up period. Another 3-month exercise programme with face-to-face, and telephone-delivered BCTs follow-up sessions will be arranged for the control group, with the number and timing of all sessions similar to that in the experimental group. All face-to-face sessions and exercise training sessions will have ≤ 10 participants to maintain good interactions between the participants and the physical trainer / facilitator.

Wearable activity tracker (WAT)-based intervention for the experimental group: The aim is to strengthen the participants' motivation to develop the intention to gradually increase their physical activity levels to eventually meet the level recommended for older people by the American Heart Association (AHA)^[2]. The intervention consists of two face-to-face group-based sessions followed by a weekly to monthly telephone sessions offering support on technical issues and behavioural change techniques.

Supervision of face-to-face sessions and telephone follow up: JL (the PI), has successfully conducted many psychosocial intervention trials to enhance behavioural changes in older people with different health problems, and RK, who has experience in using WAT with older people. They will be responsible for implementing the face-to-face sessions and training an RA as a facilitator to deliver telephone BCTs support. A protocol for the face-to-face sessions and a script for telephone behavioral support will be developed and validated by the experts in BCTs and WAT. The initial calls by the RA will be observed by JL and feedback will be provided to maintain quality. Throughout the study, the telephone support will be supervised by JL and RK.

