Frailty status: This will be assessed based on Fried's frailty five phenotypes as mentioned in the sample inclusion criteria. **Physical activity level** is one criterion of frailty that will be assessed using the 10-item PASE-C to measure self-reported occupational, household, and leisure activities for the last week.

Self-reported sedentary behavioral and physical activity: This will be assessed using the Global Physical Activity Questionnaire-Chinese version (C-GPAQ), which comprises 16 questions designed to estimate an individual's self-perceived level of physical activity in three domains (occupational, transport-related and discretionary or leisure time).

Motivation to engage in physical activity: This will be assessed by the 19-item Chinese version of the Behavioral Regulation in Exercise Questionnaire-2 (C-BREQ-2). The C-BREQ-2 is a 19-item questionnaire assessing five dimensions: amotivation, external regulation, introjected regulation, identified regulation, and intrinsic regulation. Each item is rated on a 5-point scale ranging from 0 = "not true for me" to 4 = "very true for me", with higher scores indicative of higher motivation.

Procedures: Ethical and access approval will be obtained from the Ethics Review Committee of The University and study venues, respectively. Potential participants will be referred to the research team by the community centres. An RA will screen all potential participants for their eligibility to participate in this study. Written informed consent will then be obtained from all of the participants, to whom all aspects of the study will be explained and questions answered. They will then be interviewed to obtain their demographic data, and baseline assessment. After that, the participating community centres will be randomized to either the control or experimental group. Participants from each centre will be placed into their centre's corresponding group to avoid 'contamination' effects across participants. At 1 week, 1 month, and 3 months post-intervention, an independent assessor who is blinded to the group allocations will assess the participants' outcomes, which will be compared with the baseline assessment. Another RA will collect all "Fitbit activity-related data" from the participants in the experimental group every week. All of the participants in the experimental group will be invited to attend the focus group interviews, which will be conducted by JS after the first post-test T1 and T3.

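### Only the experimental arm has a tracker that shows its own activity, so arm differences in C-GPAQ and frailty status may partly reflect reporting; the ActiGraph primary outcome is not affected

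*Protocol*

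**What the plan says.** **Who has the tracker.** The secondary outcome list in the Protocol restricts tracker data to one arm: "Fitbit Data (only participants in the experimental group): The total steps per week, total walking distance per week". Under The Control Condition, "The same physical training and BCTs support will be arranged for the control group"; no tracker is described for controls.

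**What it shows.** The Background section on the rationale for the WAT says that such devices "synchronize the data (such as step counts, time spent on MVPA, heart rate, calories burned) to smartphone applications". Self-monitoring and review of goals are among the techniques it credits to them.

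**When it is in use.** Under Interventions: "Participants will be left to use the WAT on their own for 3 months during the follow-up period". Instruments and Measures places T1, T2 and T3 at one week, one month and three months after the programme, so all three fall in that period.

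**What is self-reported.** PASE-C records "self-reported occupational, household, and leisure activities for the last week" and appears in the outcome list as the activity criterion within Frailty status. C-GPAQ estimates a "self-perceived level of physical activity in three domains" and stands under a heading that also covers sedentary behaviour. Neither is limited to one arm. For the frailty item, PASE-C counts when there is a "score in the lowest quartile (i.e., < 30 for men and < 27.7 for women"; one or two items mean pre-frail, three or more mean frail.

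**How the arms are compared.** The SAP applies a t-test or Mann-Whitney test (chi-square for categories) to the outcome variables in general. It names no questionnaire, plans no comparison of questionnaire with accelerometer, and gives no caution on self-report. The primary outcome is activity and sedentary time from an ActiGraph, worn for seven days at baseline and at each assessment.

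**The concern.** Showing people their own activity is how the tracker is meant to work. It may also change how they answer a question about their activity. From T1 onwards one arm answers with a running record to hand or in memory, and the other has no study device. A between-arm difference on C-GPAQ then mixes two effects: what people did, and what they knew about what they did. The same holds, less directly, for frailty status through its PASE-C item.

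This is a systematic difference between arms, so a larger sample would not average it away. It could inflate a C-GPAQ difference and seem to confirm the accelerometer result. It could also hide a real gain, if the tracker corrects over-reporting in one arm only. The Protocol intends to use these results to decide whether to propose a larger trial, so it matters which results can be read as changed activity.

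**Working it through.** No stated figure is involved. The total of 60 comes from a general recommendation for pilot studies, with no effect size, SD or power, so there is nothing to reproduce.

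**1. Do the planned safeguards remove the asymmetry?**
- Blinded assessor (Protocol, Procedures): no. The participant supplies the answer and knows whether a tracker is worn.
- Baseline adjustment (SAP): no. No one has a study tracker at T0, so T0 carries no information on the shift.
- Randomisation of centres: no. The asymmetry begins after allocation.

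**2. Illustration of size for a continuous score such as C-GPAQ.** Inputs: 60 participants and 1:1 allocation of centres (Protocol, Sample size), hence 60/2 = 30 per arm if centres are of equal size; alpha 0.05 (SAP), assumed two-sided; the SAP's t-test with 58 degrees of freedom; true activity equal. The reporting shift d, in SD units, is an assumption. The noncentrality is d × √(30/2) = 3.873d, the critical value is 2.002, and both tails are counted:

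| Assumed shift d | Noncentrality | Chance of p < 0.05 |
|---|---|---|
| 0 | 0 | 5.0% |
| 0.1 | 0.387 | 6.7% |
| 0.2 | 0.775 | 11.9% |
| 0.3 | 1.162 | 20.8% |
| 0.4 | 1.549 | 33.2% |

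Clustering by centre is ignored, as in the SAP's tests. The 5.0% row is therefore not this trial's true starting point. With 10 per centre and an assumed ICC of 0.01 to 0.05, the design effect is 1 + 9 × ICC = 1.09 to 1.45. The unadjusted test then rejects in about 6% to 10% of trials with no shift at all (normal approximation, 1.96 divided by the square root of the design effect).

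**3. Frailty status.** Suppose, as an assumption, that the whole PASE-C score is misreported by 10% or 20%, in either direction.
- Upward, women: the item is wrongly cleared for true scores from 27.7/1.1 = 25.2 (10%) or 27.7/1.2 = 23.1 (20%) up to 27.7.
- Upward, men: from 30/1.1 = 27.3 or 30/1.2 = 25.0 up to 30.
- Downward, women: the item is wrongly met for true scores from 27.7 up to 27.7/0.9 = 30.8 or 27.7/0.8 = 34.6.
- Downward, men: from 30 up to 30/0.9 = 33.3 or 30/0.8 = 37.5.

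Crossing the cut-off changes the frailty category only when the other four items number exactly 0 (robust versus pre-frail) or exactly 2 (pre-frail versus frail). For an upward shift, that means a participant who would otherwise have exactly 1 or exactly 3 items. The documents do not give the share of participants in these bands or with these counts, so no expected number of misclassifications follows.

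**The case against.** The strongest reply is that the main question is untouched. The ActiGraph primary outcome is measured in both arms and does not depend on recall. The affected measures are secondary, openly described as self-report, and sit in a feasibility pilot. **This stands**, and it sets the severity.

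The mechanism is also reasoned, not documented. No passage says that tracker feedback changes questionnaire answers, and the Background warns that users may not encounter the device's features at all. A tracker informs walking, active-time and perhaps sedentary items far more than household or occupational ones. **This stands** as a limit on scope.

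The contrast between arms may be softer than it looks. The step targets stand under a heading that covers both arms, and every participant must be able to use a smartphone, so some controls may count steps by phone. **This stands in part**: such counting could narrow the asymmetry, but the documents neither provide for it nor record it.

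A reader might infer more than the text allows:
- *That a significant self-report result has a 12% to 33% chance of being false.* The shifts behind such figures are assumed; the documents anchor none of them.
- *That PASE-C is a separate endpoint compromised throughout.* It appears in the outcome list only as one frailty criterion.
- *That the problem can never be examined afterwards.* Both arms wear the ActiGraph at every assessment, so the reporting gap for C-GPAQ can be described.

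**Conclusion.** The point holds for secondary outcomes only, at **low severity**. Arm differences in C-GPAQ, and in frailty status through its PASE-C item, may partly reflect tracker-informed reporting, and nothing in the plan separates this from changed activity. Size and direction are unknown; the calculated figures show sensitivity to assumed shifts and are not estimates for this trial.

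The conclusion assumes that tracker use continues to T3, as Interventions states. Instruments and Measures gives the period for monitoring tracker use as 112 days, which equals 12 × 7 + 28, whereas 12 weeks plus three months is about 84 + 91 = 175 days. The two sections should be reconciled, since tracker exposure at T3 may otherwise go unrecorded.

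The documents do not support a reading that the trial's main comparison is biased: the ActiGraph result does not pass through the participant's memory.

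**What to change.** 1. **Basis for conclusions.** State in the SAP that conclusions about changed activity rest on the ActiGraph between-arm estimate and its confidence interval, and that C-GPAQ arm contrasts are supportive only and open to differential reporting. Agreement in direction alone should not be the test: with no true effect, the ActiGraph difference falls on either side about half the time.
2. **Reporting gap.** Prespecify, by arm and visit, C-GPAQ activity and sedentary time minus the matching ActiGraph quantity, with the between-arm difference in change of this gap from T0. The SAP should name the matching quantities, their common unit and the C-GPAQ recall period, which the Protocol does not state. Do not do this for the PASE-C score, which has no common unit with ActiGraph.
3. **Frailty.** Report frailty status also without the PASE-C item, as a sensitivity analysis.
4. **Administration.** Where practical, give the questionnaires when the ActiGraph is returned, so that PASE-C's recall week is close to the measured week. Give both arms the same instruction to put away phones and any devices and answer from memory. An instruction for the experimental arm alone could unblind the assessor, who also scores the physical tests.

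**Cost.** One line in the assessor procedure, a short SAP paragraph and one or two extra tables from data already planned. Self-report results become supportive only. The gap can also vary with true activity level, so it is diagnostic and not a correction, and putting devices away does not erase what the participant already knows.
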